TITLE

Comparison of Nebulized Sub-dissociative Dose Ketamine at Three Different Dosing Regimens for Treating Acute and Chronic Painful Conditions in the ED: A Prospective, Randomized Trial

INTRODUCTION

Ketamine is a non-competitive N-methyl-D-aspartate (NMDA)/glutamate receptor complex antagonist that decreases pain by diminishing central sensitization, hyperalgesia, and “wind-up” phenomenon at the level of the spinal cord (dorsal ganglion) and central nervous system. Ketamine administration in sub-dissociative doses (0.1-0.3 mg/kg) in pre-hospital settings and in the ED results in effective pain relief in patients with acute traumatic and non-traumatic pain, chronic non-cancer and cancer pain, and in patients with opioid-tolerant pain by virtue of providing anti-hyperalgesia, anti-allodynia, and anti-tolerance. Two commonly employed strategies of SDK administration in the ED include an intravenous push (IVP) dose (over 2-5 minutes), which is associated with relatively high rates of minor but bothersome psycho-perceptual side effects (feeling of unreality and dizziness), or short infusion (SI) given over 15 minutes with significantly reduced rates of unreality and preserved analgesic efficacy.

BACKGROUND AND SIGNIFICANCE

In the situation when intravenous access is not readily available or unobtainable, sub-dissociative dose ketamine can be administered via intranasal route. The data supporting IN is not set on the optimum intranasal dose (range 0.75-1 mg/kg) and frequencies of administration. In addition, IN administration of SDK for adult patients in the ED requires a highly concentrated solutions that are not routinely stock in the ED. Hence, another non-invasive route such as nebulization via a Breath-Actuated Nebulizer which allows a controlled patient-initiated delivery of analgesics in titratable fashion (ref).

Nebulized administration of ketamine however, has only been studied in the areas of acute postoperative pain management, cancer palliation, and status asthmaticus therapy (ref). To our knowledge, there are no prospective randomized trials that evaluated a role of nebulized SDK role in managing a variety of acute and chronic painful conditions in the ED.

STUDY OBJECTIVES

To compare analgesic efficacy and rates of side effects of sub-dissociative dose ketamine administered via breath-actuated nebulizer at three different doses (0.75mg/kg, 1 mg/kg and 1.5 mg/kg) for ED patients presenting with acute and chronic painful conditions.

HYPOTHESIS

In our study we hypothesize that sub-dissociative-dose ketamine administered as a single agent via breath actuated nebulizer at the dose of 1.5 mg/kg will provide better analgesia at 30 min

post-administration with similar rates of side effects in comparison to 0.75 mg/kg and 1 mg/kg for ED patients presenting to the ED with acute and chronic painful conditions. The primary outcome of this trial is the comparative reduction in participant's pain scores at 30 minutes post medication administration.

STUDY DESIGN

Subjects: Patients 18 years of age and older presenting to the ED with acute and chronic painful conditions such as traumatic and non-traumatic abdominal, flank, back, or musculoskeletal pain as well as exacerbation of chronic abdominal, musculoskeletal and neuropathic pain with a score of 5 or more on a standard 11- point (0 to 10) numeric rating scale and requiring sub-dissociative dose ketamine analgesia, as determined by the treating attending physician. Patients' screening and enrollment will be performed by study investigators and research assistants. All patients will be enrolled at various times of the day when study investigators will be available for patient enrollment and an ED pharmacist will be available for medication preparation

Eligibility Criteria: Patients 18 years of age and older presenting to the ED with acute and chronic painful conditions such as traumatic and non-traumatic abdominal, flank, back, or musculoskeletal pain as well as exacerbation of chronic abdominal, musculoskeletal and neuropathic pain with a score of 5 or more on a standard 11- point (0 to 10) numeric rating scale.

Exclusion Criteria: Altered mental status, allergy to ketamine, pregnant patients, weight greater than 150 kg, unstable vital signs (systolic blood pressure <90 or >180 mm Hg, pulse rate <50 or >150 beats/min, and respiration rate <10 or >30 breaths/min), inability to provide consent, and past medical history of alcohol or drug abuse, or schizophrenia.

Design: This is a prospective, randomized, double-blind trial comparing analgesic efficacy and safety of nebulized SDK administered at three different doses to patients presenting to the ED of Maimonides Medical Center with acute and chronic painful conditions. Upon meeting the eligibility criteria, patients will be randomized into one of three study arms based on the dosing of the SDK: 0.75 mg/kg, 1 mg/kg, and 1.5 mg/kg.

Data Collection Procedures: Each patient will be approached by a study investigator for acquisition of written informed consent and Health Insurance Portability and Accountability Act authorization after being evaluated by the treating emergency physician and determined to meet study eligibility criteria. When English will not be the participant's primary language, a staff interpreter or licensed telephone interpreter would be used. Baseline pain score will be determined with an 11-point numeric rating scale (0 to 10), described to the patient as "no pain" being 0 and "the worst pain imaginable" being 10. A study investigator will record the patient's body weight and baseline vital signs. The on-duty ED pharmacist will prepare a breath-actuated nebulizer with doses of 0.75 mg/kg, 1 mg/kg, and 1.5 mg/kg according to the predetermined randomization list,

which will be created in SPSS (version 24; IBM Corp, Armonk, NY) with block randomization of every 10 participants. The medication will be delivered to the treating nurse in a blinded fashion and will be administered via breath-initiated nebulization with a minimum time of 5 min and maximum time of 15 min up to three doses.

Study investigators will record pain scores, vital signs, and adverse effects at 15, 30, 60, 90, and 120 minutes. If patients reported a pain numeric rating scale score of 5 or greater and requested additional pain relief, a second (equivalent to the first dose) of SDK via BAN will be administered to the patient in a blinded fashion. In situations when nebulized SDK will fail to achieve acceptable (by patient) pain relief or patient will refuse to continue nebulized SDK treatment, morphine at 0.1 mg/kg will be administered as a rescue analgesic.

All data will be recorded on data collection sheets, including patients' sex, demographics, medical history, and vital signs and entered into SPSS (version 24.0; IBM Corp) by the research manager. Development of the randomization list, confirmation of written consent acquisition for all participants, and statistical analyses will be conducted by the research manager and statistician, who would work independent of any data collection.

Patients will be closely monitored for any change in vital signs and for adverse effects during the entire study period (up to 2 h) by study investigators. Common adverse effects that are associated with sub-dissociative dose ketamine are feeling of unreality, dizziness, nausea, vomiting, and sedation.

Data Analysis: Data analyses will include frequency distributions, paired t-test to assess a difference in pain scores within each group, and independent-sample t-test to assess differences in pain scores between the 3 groups at the various intervals.

Mixed-model linear regression will be used to compare changes in pain numeric rating scale across time points. This will compensate for participants lost to follow-up and allow all patients' data to be analyzed on an intention-to-treat principle.

For categorical outcomes (eg, complete resolution of pain), a X^2 or Fisher's exact test will be used to compare outcomes at 30 minutes. Percentage differences and 95% confidence intervals between the treatment groups will be calculated for all time points with $P < .05$ to denote statistical significance. Based on the validation of a verbally administered rating scale of acute pain in the ED and the comparison of verbal and visual pain scales, we will use a primary outcome consisting of a minimal clinically meaningful difference of 1.3 between three groups at the 30-minute pain assessment.^{28,29}

Sample Size: Assuming an SD of 3.0, a power analysis determined that a repeated-measures ANOVA with a sample size of 34 patients per group (102 total) will provide at least 80% power to detect a difference of at least 1.3 at 30 minutes (as well as at any other interval post-baseline), with an $\alpha = .05$. To account for possible missing data the total sample size will be 120 patients

(40 per group). A pre-planned interim data analysis will occur upon reaching a total of total of 60 patients (20) patients per group.

Expected Outcomes: The primary outcome will include a comparative reduction of pain scores on numeric rating pain scale (NRS) between recipients of nebulized SDK at three different doses at 30 minutes post-analgesic administration.

ATTACHMENTS

List any attachments (contracts, participant materials, data collection tools, etc.)

Protocol for analgesic administration via Breath Actuated Nebulizer

MAIMONIDES MEDICAL CENTER DEPARTMENT OF EMERGENCY MEDICINE (ED)

Protocol for ED Analgesics Administration via Breath-Actuated Nebulizers (BAN)

Background

[figure not shown]
In situations when intravenous access is unobtainable or the desired dose of medications exceeds the maximum allowed dose via IM injections, alternative routes of analgesic administration play an important role in providing timely and effective analgesia in the ED. Nebulized route of analgesic administration (1) provides rapid, effective and titratable analgesic delivery; (2) results in least painful methods of analgesic delivery; (3) minimizes analgesic toxicity and side effects (opioids); and (4) improves overall management of a variety of acute painful conditions in the ED. Data supporting use of nebulized opioids (fentanyl and morphine) in the ED demonstrates comparable analgesic efficacy (overall pain relief, onset of analgesia and a need for rescue analgesia) to intravenous route. To maximize a systemic concentration of nebulized opioids and to prevent iatrogenic exposure of ED staff to opioid vapors, the use of breath-actuated nebulizers (BAN) is strongly recommended.

[figure not shown]
Breath-actuated nebulizer

The breath-actuated nebulizer (BAN, AeroEclipse, Trudell Medical International, London, Ontario, Canada) has been available as an aerosol delivery option for several years as a viable alternative to analgesic administration. This small-volume disposable nebulizer is primarily designed to generate aerosol during inspiration in response to the patient's inspiratory flow triggering the opening valve. BAN provides smaller particles and greater dose delivery efficiency than continuous jet nebulizers. This increased drug efficiency is associated with

decreased release of aerosol to the atmosphere. In addition, BAN possesses dual modes of action: (1) continuous aerosol generation; and (2) breath-actuated (in response to the patient's inspiratory flow) ensuring virtually that no drug is lost to the environment. It provides better compliance, a safer patient environment, and impacts clinical outcomes such as Length of Stay in the ED as well as better patient outcomes and reduced costs.

For ED purposes, the BAN should be placed on Breath Actuated Mode only.

Instructions for Use:

1. The equipment should be set to Breath Actuated Mode only.
2. Ensure mouthpiece is inserted into side opening of the nebulizer with the exhalation valve facing down.
3. Inspect the tubing for fray, wear or loose particulates, and ensure nothing is blocking the air supply pathway of the nebulizer
4. Unscrew and remove top of nebulizer. Place prescribed medication into nebulizer cup (maximum cup volume 6 mL). Reattach top and gently hand tighten. Medication to be prepared by the ED RN.
5. Secure the top of the nebulizer with a strip/tape that is dated and initialed by the ED RN to prevent tampering by a patient.
6. Attach one end of the supplied tubing to the fitting in the bottom of the nebulizer and the other end to the Air Source
7. Ensure both ends are securely engaged.
8. Set the flowmeter to 7 to 8 liters per minute (lpm) with an air source capable of delivering 50 PSI (344.7 kPa).
9. Instruct the patient to place mouthpiece in mouth, and inhale slowly and deeply. As patient inhales, the green feedback button on top of the nebulizer will move into the fully down position, indicating that the AEROECLIPSE* II BAN is producing aerosol in response to inhalation.

10. Patient should exhale normally: a valve on the mouthpiece opens allowing passive exhalation, as the green feedback button returns to the up position indicating no aerosol is being produced.
11. Instruct the patients to not place the lips over the exhalation valve on the bottom of the mouthpiece. Doing so will prevent the valve from functioning properly.
12. The BAN can be used for multiple rounds of medications per one patient. Once entire treatment regimen is completed, the nebulizer is to be discarded. The BAN stays with the patient for multiple doses of medications and gets discarded after the patient leaves the ED.

Indications:

Pain syndromes requiring opioid analgesia in the ED in the absence of intravenous access

Contraindications:

1. Allergy to medications
2. Altered mental status
3. Hemodynamic instability
4. Contraindications to opioids
5. Inability to follow directions
6. Patients with aberrant drug-related behaviors

Medications to be used:

1. Fentanyl:
 - a. Adults: 4 mcg/kg dose titrated q 10 min up to three doses
 - b. Pediatrics: 2-4 mcg/kg titrated q 10 min up to three doses
2. Morphine:
 - a. Adults: 10-20 mg titrate q 10-15 min up to three doses
 - b. Pediatrics: 0.2 mg/kg titrated q 10-15 min up to three doses
3. Sub-dissociative Dose Ketamine:
 - a. Adults: 0.75-1.5 mg/kg titrated q15 min up to three doses
 - b. Pediatrics (Age: older than 5): 0.75-1.5 mg/kg titrated q15 min up to three doses

Notes:

- No need for continuous cardiac and SpO2 monitoring.
- Patients should be reassessed at 10-15 minute intervals.
- Although opioid overdose using the BAN is rare, intranasal Naloxone may be used to reverse opioid overdose if it happens.

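### Side-effect rates are hypothesised to be similar across doses, but the plan sets no margin or criterion for similarity, so a non-significant result at 40 per arm could be misread as showing it

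*Combined protocol and SAP*

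**What the plan says.** All references are to the combined protocol and SAP.

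- **Study Objectives** puts side effects beside efficacy: "To compare analgesic efficacy and rates of side effects of sub-dissociative dose ketamine administered via breath-actuated nebulizer at three different doses". The verb is to compare; there is no equivalence or non-inferiority framing.
- **Hypothesis** goes further. It expects 1.5 mg/kg to relieve pain better at 30 minutes "with similar rates of side effects in comparison to 0.75 mg/kg and 1 mg/kg". The sole primary outcome is pain reduction at 30 minutes.
- **Data Collection Procedures** has adverse effects recorded at 15, 30, 60, 90 and 120 minutes. It lists unreality, dizziness, nausea, vomiting and sedation as the common ones.
- **Data Analysis** says that for categorical outcomes a chi-square or Fisher's "exact test will be used to compare outcomes at 30 minutes". The example given is complete resolution of pain; side effects are not mentioned. It continues: "Percentage differences and 95% confidence intervals between the treatment groups will be calculated for all time points", with P < .05 "to denote statistical significance". The only clinical threshold is for pain, a "minimal clinically meaningful difference of 1.3 between three groups at the 30-minute pain assessment".
- **Sample Size** rests on pain alone: "Assuming an SD of 3.0", "a sample size of 34 patients per group (102 total) will provide at least 80% power to detect a difference of at least 1.3". Enrolment is raised to 40 per group for missing data. No side-effect rate is assumed.

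**The concern.** Similarity is a positive claim and needs a statement of how large a difference would still count as similar. The plan has none. The one criterion it gives is a significance threshold for a difference. Failing to cross that threshold is weak evidence when the trial is small for the outcome, and this trial was not sized for side effects. The planned intervals would show which differences remain possible, but no rule says what interval would confirm or refute the hypothesis.

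At stake is the safety part of the trial's own hypothesis. A report could state that the highest dose had side-effect rates similar to the lower doses when the data had not excluded a material rise. The primary pain comparison is not affected.

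**Working it through.** **The plan's own figure.** There is none for side effects. The only sample size is for pain. From its stated inputs, a two-group comparison at one time point needs n = 2(1.96 + 0.842)² × 3.0² / 1.3² ≈ 84 per arm (two-sided), and 34 per arm gives 43% power. The plan names a repeated-measures ANOVA without its correlation or number of measurements, so its 34 per group cannot be confirmed or refuted. That is a separate matter and nothing below depends on it.

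**Inputs.** n = 40 per arm (Sample Size; 34/0.85 = 40). Alpha 0.05 (Data Analysis; two-sided assumed, since sidedness is not stated). Tests: uncorrected chi-square and Fisher's exact, assumed to apply to side effects. Side-effect rates: assumed, with both lower doses sharing one rate.

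**Step 1: one comparison.** Power is the sum, over all pairs of counts (x, y), of Bin(x; 40, p_high) × Bin(y; 40, p_low) wherever the test gives P < .05. The chance of a non-significant result is 1 minus this.

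**Step 2: both comparisons.** The hypothesis sets 1.5 mg/kg against each of two lower doses, so similarity would need both tests to be non-significant. The two tests share the 1.5 mg/kg arm and are correlated, so the calculation conditions on that arm's count:

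P(both non-significant) = Σₓ Bin(x; 40, p_high) × [Σ_y Bin(y; 40, p_low) × 1{P(x, y) ≥ .05}]²

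| Lower doses → 1.5 mg/kg | Power, one comparison: chi-square / Fisher | Both non-significant: chi-square / Fisher |
|---|---|---|
| 10% → 20% | 0.247 / 0.162 | 62% / 74% |
| 20% → 35% | 0.322 / 0.245 | 53% / 62% |
| 20% → 40% | 0.497 / 0.408 | 34% / 43% |

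**Step 3: what the planned intervals can show.** With equal rates, half-width = 1.96 × √(2p(1 − p)/40):

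- p = 10%: 1.96 × √(0.18/40) = 13.1 points
- p = 20%: 1.96 × √(0.32/40) = 17.5 points
- p = 30%: 1.96 × √(0.42/40) = 20.1 points
- p = 50%: 1.96 × √(0.50/40) = 21.9 points

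For illustration, suppose 8/40 against 15/40 are observed. The difference is 17.5 points and its standard error is √(0.2 × 0.8/40 + 0.375 × 0.625/40) = 0.099. The 95% interval is about −2 to +37 points. The plan does not say whether that counts as similar.

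**Step 4: if a margin were set.** With truly equal rates, the chance that the upper 95% limit for one comparison falls below a margin m is about Φ(m/√(2p(1 − p)/40) − 1.96). For an illustrative m of 15 points:

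| Rate in both arms | 5% | 10% | 20% | 30% | 50% |
|---|---|---|---|---|---|
| Chance of excluding a 15-point rise | 87% | 61% | 39% | 31% | 27% |

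The normal approximation is rough at 5%, where only two events per arm are expected. Requiring both comparisons to succeed lowers every figure.

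**The case against.** The strongest reply is that the plan is more careful than the criticism suggests. It plans intervals as well as tests. It never says that a non-significant test will be taken as similarity. The categorical-test sentence is illustrated by pain resolution and confined to 30 minutes, so applying it to side effects is the reader's inference. Pain is the only primary outcome, the objective is merely to compare side-effect rates, and an informal expectation about a secondary outcome does not always need a formal margin.

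Much of this stands, and it rules out several stronger readings that a reader might infer:

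- *That the plan offers only tests of difference.* It does not; the intervals are there.
- *That the plan's rule declares similarity whenever P ≥ .05.* No such rule is written. The misreading is a risk, not a stated procedure.
- *That the trial would probably call the highest dose similar even if it doubled side effects.* This depends on the base rate. It holds for 10% to 20% (62% to 74%) but not for 20% to 40% (34% to 43%), where at least one comparison is more likely than not to be significant. Looking at one comparison alone gives 50% to 59% for that case, which overstates the risk because the hypothesis involves two.
- *That 40 per arm cannot show similarity.* With a 5% rate and a 15-point margin, one comparison succeeds about 87% of the time.

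What the reply does not answer is that the word *similar* stands in the hypothesis and nothing in the plan says what result would support it. That side effects go unnamed in Data Analysis makes the gap wider.

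**Conclusion.** The point holds in limited form. The hypothesis claims similarity, and the plan supplies no margin, no criterion and no named side-effect analysis by which to judge it. As written, the analysis cannot validly support that part of the hypothesis, and non-significance at 40 per arm would not fill the gap. How often both comparisons would miss a real rise ranges from about a third to three quarters of trials in the scenarios examined. Those figures rest on assumed rates, equal rates in the two lower-dose arms, full data on 40 per arm, and two-sided tests at 0.05. The change is worth making because it is cheap and governs what the trial may conclude about safety. It does not touch the primary outcome.

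**What to change.** In Data Analysis:

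1. Name side effects as an outcome: any event up to 120 minutes, and each listed effect separately.
2. Report the risk difference with its 95% confidence interval for 1.5 mg/kg versus 0.75 mg/kg and versus 1 mg/kg.
3. State that a non-significant test will not be reported as similarity.
4. Choose one of two routes:
   - use *similar* only if the upper 95% limit for both comparisons lies below a margin that the investigators fix before unblinding, and otherwise report that a difference has not been excluded; or
   - restate the side-effect part of the hypothesis as descriptive estimation, without the word *similar*.

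The cost is wording only: no extra patients and no new data, since the intervals are already planned and adverse effects are already recorded to 120 minutes. The downside is a weaker safety statement, because 40 per arm will often not exclude a 15-point rise unless side effects are rare.

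### Adverse effects have no pre-dose record and no new-onset rule, so nausea, vomiting or dizziness present on arrival can be counted as side effects, which would make a true dose difference harder to see

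*Combined protocol and SAP*

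**What the plan says.** Data Collection Procedures names three items taken before dosing: a pain score on the 0 to 10 scale, and then "A study investigator will record the patient's body weight and baseline vital signs". On the sheets generally it says: "All data will be recorded on data collection sheets, including patients' sex, demographics, medical history, and vital signs". Current symptoms are not named.

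After dosing, "Study investigators will record pain scores, vital signs, and adverse effects at 15, 30, 60, 90, and 120 minutes". The same section adds that investigators watch for adverse effects throughout the study period of up to 2 hours. It lists the common effects of sub-dissociative ketamine as "feeling of unreality, dizziness, nausea, vomiting, and sedation".

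Study Objectives puts the rate of side effects beside analgesic efficacy. The Hypothesis section expects the 1.5 mg/kg arm to give better analgesia "with similar rates of side effects in comparison to 0.75 mg/kg and 1 mg/kg", and states no margin for similarity.

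Data Analysis plans chi-square or Fisher's exact tests for categorical outcomes, and percentage differences with 95% confidence intervals at all time points. The example it gives is complete resolution of pain. It has no definition of a treatment-emergent effect, no attribution rule and no adjustment of adverse effects for baseline.

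**The concern.** Three things are recorded at each follow-up time: pain, vital signs and adverse effects. The first two have a stated baseline and the third does not. The eligible patients include those with traumatic and non-traumatic abdominal and flank pain, who may well arrive nauseated, vomiting or dizzy. Nothing in the plan separates a patient who arrived nauseated and is still nauseated at 15 minutes from one whose nausea began after the nebulizer.

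The comparison of side-effect rates between doses is at stake. Randomization balances presenting symptoms in expectation, and blinding keeps recording even-handed. Neither removes a background of pre-existing symptoms that, if counted, sits in every arm and masks part of any real difference. Because the plan hopes to find similar rates, the masking works in favour of its own hypothesis.

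**Working it through.** The documents give no side-effect rate and no prevalence of symptoms at presentation, so there is no figure of the plan's own to reproduce. The sample size calculation concerns the pain score and does not bear on this point.

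**Inputs**
- From Sample Size: n = 40 per arm. From Data Analysis: significance at P < .05, taken as two-sided.
- Assumed: new-onset rates r of 20% and 40% in two arms, among patients without the symptom at entry.
- Assumed: a share b of each arm, the same in both, has the symptom at entry (15%, 30% or 45%).
- Assumed: under the first count below, every such patient still has the symptom after dosing and is counted.

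**Formulas**
- Presenting symptoms counted: rate = b + (1 − b)r.
- New onset only, over all randomized patients: rate = (1 − b)r.
- Risk difference under either count: (1 − b)(0.40 − 0.20). The term b cancels in the first.
- Power: h = 2·arcsin√p₂ − 2·arcsin√p₁, and power ≈ Φ(h√(n/2) − 1.96), with √(40/2) = 4.472.

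**Reference case, b = 0:** 20% vs 40%, h = 0.442, and 0.442 × 4.472 − 1.96 = 0.017, so power is 51%.

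**Worked case, b = 15%**
- Counted: 0.15 + 0.85 × 0.20 = 32% and 0.15 + 0.85 × 0.40 = 49%. h = 0.348, and 0.348 × 4.472 − 1.96 = −0.40, so power is 34%.
- New onset only: 0.85 × 0.20 = 17% and 0.85 × 0.40 = 34%. h = 0.395, and 0.395 × 4.472 − 1.96 = −0.19, so power is 42%.

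| b | Presenting symptoms counted | Risk ratio | Power | New onset only | Risk ratio | Power | Risk difference, both counts |
|---|---|---|---|---|---|---|---|
| 15% | 32% vs 49% | 1.53 | 34% | 17% vs 34% | 2.00 | 42% | 17 points |
| 30% | 44% vs 58% | 1.32 | 24% | 14% vs 28% | 2.00 | 34% | 14 points |
| 45% | 56% vs 67% | 1.20 | 17% | 11% vs 22% | 2.00 | 27% | 11 points |

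The direction does not depend on the assumed rates. At b = 30%, true rates of 10% vs 30% would be observed as 37% vs 51% (risk ratio 1.38 instead of 3.00), and 30% vs 60% as 51% vs 72% (1.41 instead of 2.00).

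The new-onset rule leaves the risk difference over all patients unchanged. It removes the common background, which restores the risk ratio and lowers the binomial variance in this example. The power gain is about 8 to 10 percentage points.

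**The case against.** The strongest reply is that the plan is silent, not wrong. It says investigators record adverse effects, which is not the same as every symptom present. A blinded investigator may well leave out nausea that preceded the drug. A reader might infer that presenting symptoms will be scored as ketamine effects, but no section says so. What stands is that nothing prevents it, and that unwritten judgement may differ between investigators.

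The data collection sheet is not reproduced, and the list of its contents is not presented as exhaustive, so a baseline symptom row may exist. Medical history and the treating physician's evaluation before enrolment may also capture some presenting symptoms. It would therefore go too far to say that the information could never be recovered. It would still be less reliable than a check at time 0, and the plan provides for no comparison with it.

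The reply also narrows the scope. Altered mental status is an exclusion, so sedation, and probably unreality, are unlikely before dosing. The five listed effects are described as common, not defined as a composite endpoint. Monitoring through the whole period means that 15 minutes is only the first scheduled record, but it supplies no pre-dose one.

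Finally, the primary outcome, pain at 30 minutes, is unaffected. The lack of a similarity margin and the low power even at b = 0 (51% in this example) limit the safety conclusion at least as much. Both points are fair, and they bear on priority; the gap remains.

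**Conclusion.** The point holds as a gap in measurement and definition, mainly for nausea, vomiting and dizziness. Presenting symptoms can be counted as side effects. If they are, rates are inflated in every arm and a true dose difference becomes harder to see. In the illustration the risk ratio falls from 2.0 to between 1.5 and 1.2, and power is 34% to 17% against 42% to 27% with new-onset counting.

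These sizes rest wholly on assumed rates and prevalences, equal prevalence in the arms, and full persistence and counting of presenting symptoms. The documents fix only the 40 per arm and the .05 level.

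Two stronger readings are tempting, and neither is supported:
- A reader might infer that the result is pushed toward similarity whether or not the doses differ. It is not: with no true difference, (1 − b) × 0 = 0. Masking needs a real difference to mask. In a single trial, chance imbalance in presenting symptoms could also push the comparison either way.
- A reader might set 51% against 17% and take that as the loss the fix would recover. The 51% belongs to a population with no presenting symptoms. New-onset counting in the actual population leaves the risk difference at 17, 14 or 11 points and recovers only part of the power.

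The change is worth making because a stated objective is affected and analysts cannot reliably supply the missing record later.

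**What to change.** In Data Collection Procedures, add the symptom checklist used at follow-up to the baseline assessment, before the first inhalation. It should cover at least nausea, vomiting and dizziness; using all five listed effects keeps the form uniform. Define a side effect as a symptom absent at baseline and present at any time after the first dose. In Data Analysis, state that between-arm side-effect rates use this definition with all randomized patients in the denominator, and report baseline symptom prevalence by arm.

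Count worsening of a pre-existing symptom only if a simple severity grade is recorded at baseline and at every later time. The plan has no such grade now, and a baseline tick alone cannot support it.

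The cost is one extra row on the sheet, completed by the investigator who already takes baseline pain and vital signs. Adding the severity grade would cost an entry at each of the five later times as well. Reported rates will be lower than a raw symptom count, so the report should state the definition beside them. The sample size and the primary analysis do not change.
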